6.1. General points and methodology

✓ Methodology — trial design

Prospective, multicenter, randomized, controlled, open-label study, with blind evaluation of the primary criterion and several secondary criteria (PROBE design).

Parallel group design (1:1):

- The arm receiving the device under investigation: PA1704
- The arm receiving the comparator medical device: BioRoot™ RCS.

✓ Measures to reduce or avoid bias.

Randomization and stratification:

Before the trial is set up, the CRO's biostatistician will computer-generate a block randomization list stratified by clinical indication (initial endodontic treatment (ET) versus re-treatment (ER)). The randomization system will be integrated directly into the electronic CRF.

Randomization will be carried out by the electronic CRF once the eligibility criteria have been checked, the clinical indication (ET or ER) has been determined and all this information has been recorded in the specific module by the investigator.

It should be noted that the proportion of ERs will be 30% of the overall sample, which is close to the rate reported in a French Health Insurance survey (Masson 2002). The rate of ER may vary between sites: some investigators, because of their specialty in endodontics, will include a majority of patients with an indication for re-treatment, whereas GP investigators will probably have more indications for first-line treatment.

Blind:

Investigators and patients will not be blind to the medical device allocated due to the different ways in which the 2 products are presented and used. On the other hand, two independent qualified assessors (previously calibrated under the supervision of the study coordinator) will conduct the blind, centralized review of the retro-alveolar X-rays taken at TO (reference radiograph obtained immediately post-operatively), 6 months, 12 months, 24 months, 3.5 years and 5 years (Refer to Section "Equipment to be used to evaluate clinical trial variables and arrangements for monitoring maintenance and calibration." section of this chapter); they will be blinded to centre, patient, indication (initial or repeat endodontic treatment), and treatment arm; the files will first be anonymized by the CRO.

✓ Outcome measures

Primary criterion (composite criterion):

The primary criterion is the **2-year efficacy rate of endodontic treatment** based on radiological criteria assessed blind by independent reviewers (complete healing, reduction of lesions, failure) AND clinical criteria assessed by the investigator (tooth functionality and pain).

Secondary criteria:

Reminder of secondary objectives	Secondary outcome measure	Time of evaluation (assessor)
Evaluation of the 6-month efficacy rate determined on the basis of radiological and clinical criteria	Radiological criteria (complete healing, reduction of lesions, failure) AND clinical criteria (tooth functionality and pain)	6 months (radiological criteria assessed by blind reviewers; clinical criteria assessed by investigator)
Evaluation of the 12-month efficacy rate based on radiological and clinical criteria	Radiological criteria (complete healing, reduction of lesions, failure) AND clinical criteria (tooth functionality and pain)	12 months (radiological criteria assessed by blind reviewers ; clinical criteria assessed by investigator)
Assessment of the 3.5-year efficacy rate of the endodontic treatment determined on the basis of radiological and clinical criteria (PA1704 arm only)	Radiological criteria (complete healing, reduction of lesions, failure) AND clinical criteria (tooth functionality and pain)	3.5 years ± 6 months (radiological criteria assessed by reviewers blind to the centre; clinical criteria assessed by the investigator)
Evaluation of the 5-year efficacy rate on the basis of radiological and clinical criteria (PA1704 arm only)	Radiological criteria (complete healing, reduction of lesions, failure) AND clinical criteria (tooth functionality and pain)	5 years ± 6 months (radiological criteria assessed byreviewers blind to the centre; clinical criteria assessed by the investigator)
Radiological evaluation of the quality of the apical filling (in terms of the level of apical filling, density and resorption of the extruded material)	Level of obturation at the X-ray apex (complete obturation, under-filling or over-filling)	T0 immediate post-op (investigator)
	Density: radiopacity and presence of vacuity	T0, 6 months, 12 months, 24 months for the 2 arms, And 3.5 years, 5 years for the PA1704 arm. (investigator + blind reviewer)
	Resorption of extruded material in the periapical space in the event of over-filling	6 months, 12 months, 24 months for the 2 arms, And 3.5 years, 5 years for the PA1704 arm. (investigator + blind reviewer)
Description of the pain experienced by the patient in the 7 days post-operation.	Preoperative pain (VAS 0-100 mm), Post-operative pain at different times after root canal obturation, Maximum post-operative pain felt between T0 and 7 days, Time to onset of maximum pain	Preoperative (at the start of each endodontic treatment session, i.e. 1 or 2 sessions for root canal preparation and obturation), TO (end of endodontic treatment), T12h (or before going to bed or getting up the next day depending on the time at TO), T24h, T48h, T72h and 7 days (patient, investigator)

	T =	T , , , , , , , , , , , , , , , , , ,
Description of the use of oral painkillers in the 7 days following	Classes of painkillers,	T0 to D7 (patient, investigator)
surgery	Reason for use,	
	Frequency of painkiller intake,	
	Cumulative dose over 7 days	
	Proportion of patients who used an oral painkiller between T0 and D7	
Evaluation of adverse events following endodontic treatment	Proportion of patients with at least 1 AE	Continuously from T0 to 24 months for the BioRoot™ RCS
	Number of AEs;	arm, and 5 years for the PA1704 arm(investigator)
	Type of AE, intensity, level of attribution to the filling material or surgical technique.	
	Number of additional dental consultations for complications or significant postoperative pain.	
	Number of faults and description.	
Description of the surgical technique for first-line endodontic treatment (ET) or repeat endodontic treatment (RET) and any perioperative complications,	Type of anesthesia,	T0 (investigator)
	Technique for removing the old filling material (ER only),	
	Type of endodontic instruments used to shape the canal,	
	Type of disinfectant and rinsing solutions used and solution activation technique used,	
	Gutta-percha condensation technique,	
	Coronal restoration technique,	
	Description of any intra-operative complications.	
Evaluation of operator comfort and satisfaction with the use of the material	Comfort, practicality of handling the device, ease of applying the material, difficulties encountered, time, reproducibility of root canal preparation and obturation,	TO (CRF— investigator) then at the end of the trial (overall satisfaction questionnaire — investigator)
	Advantages and disadvantages of the ready-to-use form compared with the powder-liquid form.	
	Overall practitioner satisfaction.	

Table 3: List of secondary outcome measures.

✓ Methods and times for evaluating, recording and analyzing variables.

Measurement time and people in charge of evaluation:

For each criterion, this information is given in the table above.

Generally speaking, the assessment of performance and safety criteria begins with the root canal obturation.

Method of evaluating the efficacy rate of initial or repeat endodontic treatment (at 6 months, 12 months and 24 months for the 2 arms; and 3.5 years and 5 years for the PA1704 arm):

Therapeutic efficacy is a composite criterion based on the radiological data assessed **in blind conditions** by reviewers AND on the clinical data assessed **in an open-label manner** by the investigator at the follow-up visits at 6 months, 12 months, 24 months, 3.5 years and 5 years (only the PA1704 arm for the last 2 visits). With regard to the blind evaluation of the radiological criteria by two independent reviewers, the following clarifications are provided:

- The reviewers shall examine the anonymized retro-alveolar images (JPEG files as described in the imaging procedure in section "Equipment to be used to evaluate clinical trial variables and arrangements for monitoring maintenance and calibration." of this chapter) and answer the following questions:
 - Apical lesion: 1) Presence, absence or appearance of a lesion compared with the TO reference image? 2) In the case of a pre-existing lesion at TO, what is the evolution of the size of the lesion (reduction, stabilization or increase)?
 - Root canal filling density: 1) Is the radiopacity sufficient? 2) Presence of at least one bubble in the filling material?
 - Resorption of extruded material where applicable: Is the extruded material still present in the apical space?
- Timetable: 5 centralized image review campaigns are planned, one before each statistical analysis:
 - o 1st review campaign: At the end of the 6-month follow-up of all enrolled patients, a blind review of the T0 reference image and the 6-month follow-up image,
 - o ^{2nd} campaign: after 12 months' clinical follow-up of all patients, blind review of the 12-month check-up image,
 - o 3rd campaign: After 24 months of clinical follow-up for all patients, a blind review of the 24-month check-up image,
 - 4th campaign: After approximately 3.5 years of clinical follow-up of the patients treated with the PA1704 MD, a centre-blind review of the 3.5-year follow-up image,
 - o 5th campaign: After approximately 5 years of clinical follow-up of the patients treated with the PA1704 MD, a centre-blind review of the 5-year follow-up image.

By combining the responses relating to the radiological and clinical criteria, 3 levels of treatment efficacy are obtained: Effective treatment, Ineffective treatment, Efficacy uncertain (see table below).

Treatment efficacy will be evaluated using 2 complementary approaches:

- Main analysis on soft criteria: the rates of effective or uncertain treatment are compared with the rates of ineffective treatment,
- Secondary analysis based on strict criteria: rates of effective treatment are compared with rates of uncertain or ineffective treatment.

ТО	Check-ups at 6, 12 and 24 months							
Radiological criteria	Radiological criteria (blind reviewer)	Clinical criteria (investigator)	Conclusion Treatment efficacy rate					
No lesions	No lesions (complete healing)	asymptomatic, functional tooth	Effective treatment					
No lesions	Appearance of lesion (failure)	asymptomatic, functional tooth	Ineffective treatment					
No lesions	Appearance of lesion (failure)	symptomatic, non- functional tooth	Ineffective treatment					
Presence of lesion	No lesions (complete healing)	asymptomatic, functional tooth	Effective treatment					
Presence of lesion	Reduction in lesion size (incomplete healing)	asymptomatic, functional tooth	Effective treatment					
Presence of lesion	Reduction in lesion size (incomplete healing)	symptomatic, non- functional tooth	Efficacy uncertain					
Presence of lesion	Stabilization of lesion size	symptomatic or non- functional tooth	Ineffective treatment					
Presence of lesion	Stabilization of lesion size	asymptomatic tooth, functional tooth	efficacy uncertain					
Presence of lesion	Increase in lesion size (failure)	symptomatic or non- functional tooth	Ineffective treatment					
Presence of lesion	Increase in lesion size (failure)	asymptomatic tooth, functional tooth	Ineffective treatment					

Table 4: Evaluation of the efficacy of endodontic treatment based on clinical and radiological criteria.

✓ Equipment to be used to evaluate clinical trial variables and arrangements for monitoring maintenance and calibration.

Apart from the radiology equipment connected to a computer, no specific equipment is needed to collect the outcome measures.

Retro-alveolar X-rays are taken with an angulator using the parallel planes technique; the **entire tooth should be visible in the image** (crown to apex, passing through the root). There are no other specific settings imposed for the devices.

The images will be converted to .jpg format, without filters, and anonymized before being uploaded to the eCRF.

✓ Procedures for replacing subjects, if necessary.

See Chapter 7.4

6.2. Medical devices under investigation (ready-to-use material PA1704) and comparator (BioRoot™ RCS powder-liquid material)

✓ Comparator Medical Device Description — BioRoot™ RCS:

The selected comparator MD was the BioRoot™ RCS permanent root canal filling material.

BioRoot™ RCS is a Class III implantable medical device for dental use manufactured by Septodont. BioRoot™ RCS is based on Active Biosilicate Technology (ABS). It is a mineral root canal cement composed mainly of tricalcium silicate, zirconium oxide and calcium chloride. It comes in the form of **two products (powder-liquid) that are to be mixed**. Clinical indications, contraindications, characteristics, instructions for use, warnings, storage and disposal procedures are detailed in the instructions for use (see Annexe 3).

Thus, the medical device under investigation (PA1704) and comparator device (BioRoot™ RCS) are 2 calcium silicate-based cements, which are used for the same endodontic indications but come in 2 different forms, as a powder-liquid mixture or as a ready-to-inject paste. The 2 medical devices are similar and the aim of this study is to show that the performance and safety of the new material are not affected by the change in presentation.

✓ Exposure to medical devices under investigation and comparator

Patients included in the study will randomly receive one of 2 filling materials, PA1704 or BioRoot™ RCS, to treat one tooth (one or more root canals depending on the type of tooth affected by pulpal disease). The medical device is administered (implanted) only once, on the day of the endodontic treatment. The material is implanted for the long term, as it is intended to seal the root canals permanently. It is not intended to be removed during the trial, nor after the end of the trial, except where the treatment has failed with an indication to restart treatment.

✓ List of any other medical devices or medicines to be used during the clinical investigation.

Initial or repeated endodontic treatment is a surgical procedure that involves several stages and requires the use of several surgical instruments, solutions and filling materials. Several endodontic techniques exist for the preparation and filling of a root canal; these are authorized for trial purposes and practitioners shall maintain their usual practice.

The medical devices and medicines used are:

- Instruments available for shaping the canal: all types of file or broach, manual or mechanical (continuous or alternating rotation system, with or without apex locator).
- Irrigation solutions used to clean the canal:
 - Disinfectant solutions: sodium hypochlorite (NaOCI, mandatory), Chlorhexidine (not systematic),
 - Chelating rinse solutions: EDTA, HEDP, citric acid or other solutions. Solution activation techniques may vary (sonic system, ultrasound, Erbium Yag laser, other laser, other).
- A neutral, semi-solid, compactable filling material to be combined with the luting cement: a master cone of gutta-percha (single cone technique) or several cones of gutta-percha (cold lateral condensation technique).
- Watertight coronal reconstruction material: glass ionomer cement or bonded composite (the use of a temporary cement such as Cavit® is strongly discouraged and the use of IRM® cement is not authorized within the framework of this trial).

✓ Number of devices under investigation to be used and their justification.

A total of 80 patients will receive PA1704 (single dose, amount required for a monoradiculated or multiradiculated tooth) and 80 patients will receive BioRoot™ RCS (single dose, amount required for a monoradiculated or multiradiculated tooth).

Number of PA1704 MD to be used: 1 syringe of 0.5 g of cement can seal up to 5 canals. One syringe will be used for a single patient. **80 syringes will have to be used**.

Number of Bioroot™ RCS MD to be used: bearing in mind that one kit can seal 35 canals (i.e. 1 kit used for several patients) and that a vial of powder can be kept for 6 months after opening, 2 BioRoot™ RCS kits will be needed in each investigating center to cover the 9-month recruitment period.

Delivery of MDs to centers: 2 BioRoot™ RCS kits and 15 PA1704 syringes will be delivered to each investigating center at the set-up visit; sachets containing additional caps, grip wings and endodontic tips will also be provided. Depending on the number of patients included, the number of canals to be filled, any device defects and the products' validity date, additional medical devices will be delivered to the investigating practices if necessary.

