2.1. General synopsis of the clinical trial

Study title	Evaluation of the Efficacy Rate of Endodontic Treatment at 2 Years After Root Canal Filling With a Ready-to-use Root Canal Sealer PA1704 Versus BioRoot™ RCS: a Randomized Controlled Trial.	
Keywords	Endodontic treatment; endodontic retreatment; permanent root canal sealer (cement)	
Methodology / Study design	Multicenter, prospective, randomized, open-label and blind study to asset the primary criterion (PROBE design). PA1704 versus BioRoot™ RCS non-inferiority study.	
Study schedule	Duration of recruitment period: 9 months, Expected duration of participation for each subject: 24 months (BioRoot™ RCS arm) or 5 years (PA1704 arm), Total planned duration of the clinical trial: 5 years and 9 months.	
Medical devices being studied	This study relates to 2 implantable dental medical devices. PA1704 and BioRoot™ RCS are 2 permanent root canal filling materials for initial or repeated endodontic care, manufactured by Septodont. These are tricalcium silicate-based cements; they come in 2 different formats and are used in combination with gutta-percha:	
	 PA1704 is the medical device under investigation: Class IIa MD available in ready-to-use format; the cement is prepared in a syringe. BioRoot™ RCS is the medical device comparator: Class III MD, CE marked and used in accordance with the instructions. It comes in a mixing box comprising of a vial of powder composed of tricalcium silicate, zirconium oxide and povidone and an aqueous solution of calcium chloride and polycarboxylate. The powder and liquid must be mixed extemporaneously by the dental surgeon to form the cement. 	
Aims of the study	The aim of the clinical trial is to evaluate the performance and safety of the PA1704 ready-to-use filling material compared to BioRoot™ RCS cement. Main objective: Evaluation of the 24-month efficacy rate of endodontic treatment	
	determined on the basis of radiological and clinical criteria. Secondary objectives:	
	 Evaluation of the 6-month efficacy rate determined on the basis of radiological and clinical criteria, Evaluation of the 12-month efficacy rate determined on the basis of radiological and clinical criteria, Assessment of the efficacy of the PA1704 ready-to-use filling material at 3.5 and 5 years, determined on the basis of radiological and clinical criteria. Radiological assessment of the quality of the apical filling: 	

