2.11. Warnings

- In the root canal, the length of the working area should not exceed 2 mm from the X-ray apex to avoid apical extrusion.
- Do not bend the end cap too much to prevent breaking it.
- In the event of skin or eye contact, the product may cause irritation. Do not handle the device without appropriate personal protective equipment.
- Use a dam to ensure that the cement does not touch the mucosa and is not swallowed.
- Do not use a hot filling technique. If this technique is used, the technical specifications are not guaranteed.
- Using PA1704 without gutta-percha cones will compromise endodontic and retreatment procedures.

2.12.**Storing PA1704:**

Store PA1704 below 30°C, away from moisture.

Do not exceed the expiry date shown on the outer packaging. The product is currently valid for: 24 months from date of manufacture.

Note: Batch validity tests are currently carried out by SEPTODONT in line with Directive 2003/94/EC, which defines Good Manufacturing Practice. To date, the results obtained indicate a validity period of 24 months. The validity date will be updated as and when required.

2.13. Disposal of products:

Disposal of waste (excess cement, tips, packaging): no specific recommendations; dispose of these in accordance with your usual procedures.

Disposal of PA1704 syringes: store syringes used for treatment and defective syringes in the collection box provided by the CRO; these are to be collected at the end of the clinical trial.

3. Rationale for the design of the clinical trial

3.1. General information on endodontic treatment and cements:

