- **Retro-alveolar X-ray check** to evaluate the results of endodontic treatment at 24 months: 1) density of the root canal filling (radiopacity + presence of voids), 2) progress of resorption of the extruded material where appropriate, 3) apical lesion (absence/appearance/still present compared with TO) and progress of the size of an existing lesion (reduction, stabilization or increase).

Upload the 24-month follow-up retro-alveolar image to the eCRF (reminder: the entire tooth – from the *crown to the apex, including the root* – must be visible in the image; see Chapter 6.1).

— Where appropriate (in the event of the appearance of a lesion or an increase in the size of a pre-existing lesion), notification of ET failure by the investigator: schedule retreatment.

For patients in the PA1704 group whose endodontic treatment is effective at 24 months: Offer to continue clinical follow-up for up to 5 years: Inform patients about the study (dedicated information note) and provide them with a consent form.

— Complete the end-of-study form at the end of the eCRF for patients whose clinical follow-up has been completed (all patients in the BioRoot™ RCS group are followed-up with for up to 24 months, and patients in the PA1704 group who decline to continue the clinical follow-up for up to 5 years or for whom treatment failure is notified at 24 months).

PA1704 arm: V6 — Clinical follow-up visit at 3.5 years (± 6 months) — Standard practice

- **Clinical examination**: Verification of the functional status of the treated tooth and percussion test (lateral and axial),
- Recording of AEs.
- **Retro-alveolar X-ray check** to evaluate the results of endodontic treatment at 3.5 years: 1) density of the root canal filling (radiopacity + presence of voids), 2) progress of resorption of the extruded material where appropriate, 3) apical lesion (absence/appearance/still present compared with T0) and progress of the size of an existing lesion (reduction, stabilization or increase).

Upload the 3.5-year follow-up retro-alveolar image to the eCRF (Reminder: The entire tooth – from the *crown to the apex, including the root* – must be visible in the image; refer to Chapter 6.1).

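### The reason given for open-label use covers the operator but not the patient, so patient-reported pain and safety comparisons carry expectation bias that could be reduced

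*Combined protocol and SAP*

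**What the plan says.** The design is described in section 6.1 as an "open-label study, with blind evaluation of the primary criterion and several secondary criteria (PROBE design"). The paragraph on blinding then states: "Investigators and patients will not be blind to the medical device allocated due to the different ways in which the 2 products are presented" and, the sentence continues, used. On the device side, only the central X-ray reading is blinded. Section 16 repeats that the products are not blinded, and section 6.5.4 lists no foreseeable factor that could compromise interpretation.

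The difference between the products is one of format. Section 6.2 says they are "used for the same endodontic indications but come in 2 different forms, as a powder-liquid mixture or as a ready-to-inject paste". For the comparator, the synopsis says: "The powder and liquid must be mixed extemporaneously by the dental surgeon to form the cement".

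The patient fills in a booklet covering pain, painkillers and adverse events for 7 days (6.5.2). Section 7.7.5 tests pain between arms at each time point, along with maximum pain, its time of onset and the proportion using an oral painkiller. Section 7.7.6 compares adverse events and extra dental consultations.

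The primary criterion joins the blinded X-ray reading to a clinical part: "AND clinical criteria assessed by the investigator (tooth functionality and pain"). The synopsis adds that pain at visits comes from interviewing the patient as well as from percussion.

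**The concern.** One reason is used for two different people. The dentist cannot be unaware of whether a powder was mixed or a syringe used. The patient's position is different: both sealers are placed inside the canal with gutta-percha, and the plan never says why the patient has to know which one was used.

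This matters because the patient produces the data most sensitive to expectation. PA1704 is being used in humans for the first time (3.3) and its adverse effects in patients are described as unknown (5.4). A patient who knows that the new material was placed, or the established one, may rate pain, take analgesics, report events or seek a consultation differently. No analysis in section 7 can separate such an effect from a true difference between sealers.

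**Working it through.** **1. Does the stated reason reach the patient?**

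- Operator: Table 5 (6.5.1) has about 60 seconds of mixing, then application by cone or lentulo spiral, for BioRoot RCS. PA1704 is injected from a syringe. The operator necessarily knows the arm.
- Patient: cone insertion, cutting, condensation, X-ray and coronal restoration follow in both arms. Section 2.11 adds for PA1704: "Use a dam to ensure that the cement does not touch the mucosa and is not swallowed". That dam protects the mucosa and is not a visual screen. The documents do not say what the patient can see or recognise.
- Later visits: the first step that openly depends on the arm is at V5: "For patients in the PA1704 group whose endodontic treatment is effective at 24 months: Offer to continue clinical follow-up for up to 5 years". It comes with its own information note and consent form, so it need not reveal the arm before the 24-month assessment.
- Disclosure routes before V5: (a) the identifier in 6.6.4 contains N or R for the arm and is used on the follow-up booklet; (b) for exclusive endodontists, 6.5.2 sends a treatment report to the patient's regular dentist, who returns function, percussion and adverse event data. Table 5 also gives different waiting times before an anchor pin (7 days for PA1704; 1 week to 1 month for BioRoot RCS), so that dentist may learn the arm.

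**2. Does masking change the sample size?**

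Inputs from 7.2 and 7.3: 90% in both arms, margin 13 points, one-sided 5%, 80% power.

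n = 2 × 0.90 × 0.10 × (1.645 + 0.842)² / 0.13² = 65.85, rounded up to 66, as stated. Then 66 × 1.2 = 79.2, rounded up to 80, also as stated. Masking patients alters none of these inputs.

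**3. Illustration for 7-day pain.**

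The documents give no VAS SD and no expectation effect, so both are assumed. With 80 per arm, SE = SD × √(2/80), and the two-sided 5% rejection rate for a pure shift d is Φ(d/SE − 1.96) + Φ(−d/SE − 1.96). For SD 25 mm, SE = 3.95 mm. With d = 5 mm, d/SE = 1.265 and the rate is 24.4%.

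| Assumed shift | SD 20 mm | SD 25 mm | SD 30 mm |
|---|---|---|---|
| 3 mm | 15.8% | 11.8% | 9.7% |
| 5 mm | 35.3% | 24.4% | 18.4% |
| 10 mm | 88.5% | 71.6% | 55.9% |

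A shift in the opposite direction could mask a real difference of the same size.

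**4. How far do symptoms reach the primary endpoint?**

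Under the soft definition in 6.1, effective and uncertain both count as success. Reading the rows of Table 4:

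| X-ray finding | Asymptomatic, functional | Symptomatic and/or non-functional, as listed | Soft result changes? |
|---|---|---|---|
| No lesion at follow-up | Effective | Not listed | Not defined |
| New lesion | Ineffective | Ineffective | No |
| Reduced lesion | Effective | Uncertain | No |
| Stable lesion | Uncertain | Ineffective | Yes |
| Enlarged lesion | Ineffective | Ineffective | No |

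Under the strict definition, the reduced-lesion row is the one that depends on symptoms. Symptoms also enter through early failures: at 6 or 12 months, the unblinded investigator may declare failure for a new or enlarged lesion judged an emergency, with a symptomatic tooth as the example. That failure is carried forward to 24 months (6.5.2).

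For scale, on assumed inputs: if a share s of teeth have a stable lesion and expectation shifts their symptom classification by b between arms, the soft difference moves by s × b. With s from 2% to 15% and b from 5 to 30 points, this is 0.1 to 4.5 points. At 66 per arm:

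- In favour of PA1704, the one-sided error at the margin (77% versus 90%) rises from about 5% to between 5.2% and 18.4%.
- Against PA1704, power at 90% in both arms falls from 80% to between 79% and 44%.

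These figures combine patient and investigator effects. Patient masking would remove only part of them.

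**The case against.** The open-label PROBE design is disclosed, and the radiological component is read blind. The non-inferiority conclusion rests on the 24-month primary analysis alone (7.7.8). The 7-day pain objective is worded as description, although 7.7.5 does test it. These points stand, and they keep this well short of a threat to the main conclusion.

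A reader might infer three stronger things, none of which the documents support.

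- **That the stated reason applies to the operator alone, so the bias is wholly avoidable.** Section 6.1 cites use as well as presentation, and an awake patient may notice mixing or a lentulo spiral. Masking is plausible but not shown to be feasible, and some patients will guess.
- **That half of the primary endpoint is compromised.** Table 4 shows otherwise for the soft analysis. The investigator who examines the tooth and calls early failures also stays unblinded, so masking patients reduces bias there without removing it. The same holds for attribution of adverse events.
- **That the VAS percentages estimate the bias in this trial.** They are rejection rates for whatever shift is assumed.

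The letter N or R on the booklet does not explain itself to a patient. It is still an avoidable disclosure route.

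**Conclusion.** The point holds in limited form. The plan justifies an unblinded operator and gives no separate justification for an unblinded patient. Patient-reported 7-day pain, painkiller use, adverse event reports and extra consultations are compared between arms and are open to expectation bias that could be reduced at modest cost. Its direction and size are unknown. A 24% false-significance rate for a 5 mm shift is an illustration that rests on an assumed SD of 25 mm, 80 patients per arm and a single VAS comparison.

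The effect on the primary endpoint is limited, and only partly reachable by masking patients. Dealing with the rest would need a separate safeguard for the clinical examination. The conclusion assumes that patients can, at least in part, be kept unaware; the documents neither show nor exclude this.

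**What to change.** - **6.1:** state that investigators are unblinded. Patients are not told the allocated sealer, and it is prepared out of their view where feasible, until the V5 clinical assessment has been recorded. The PA1704 extension offer follows that assessment. Align the statement in section 16.
- **6.6.4:** remove the N/R letter from the identifier used on the follow-up booklet and on any other patient-held document.
- **6.5.2, letter to the regular dentist:** ask that the allocation not be disclosed to the patient.
- **D7 call and V5:** record, after the outcome data have been taken, whether the patient knows or has guessed the arm.
- **If the sponsor considers masking unworkable:** give the patient-specific reason in 6.1.
- **Reporting:** label any false-significance figures for VAS as illustrations on an assumed SD and shift.

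Cost: site briefing, recoding of identifiers and revised wording of the letter and patient-held documents. Some patients will still guess or ask. The sample size is unchanged, and the investigator continues to know the arm.
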